1.1.5 The Role of IL-18 in Crohn's Disease

The first evidence for the role of IL-18 in inflammatory bowel disease was provided by (Pizarro, Michie et al. 1999). This study revealed an upregulation of IL-18 in the intestine of patients with CD with a higher expression in active disease and a localization of IL-18 synthesis in intestinal epithelial cells (IECs) as well as macrophages and dendritic cells (DCs) in the lamina propria. Functional data followed this initial descriptive study indicating that mice were protected in various models of colitis, including dextran sulfate sodium (DSS)- and trinitrobenzene sulphonic acid (TNBS)-induced colitis, when either pro- IL-18 could not be activated or the active cytokine was neutralized via antibody (Kanai, Watanabe et al. 2001) (Siegmund, Rieder et al. 2001). In agreement with the human data, IL-18 production was localized to IECs and macrophages or DCs of the lamina propria. At that time, one could conclude that neutralisation of IL-18 should be beneficial for intestinal inflammation. Conflicting data were reported by other laboratories and IL-18 deficiency was shown to result in severe colitis (Takagi, Kanai et al. 2003). When experimental colitis was induced (by DSS) in NIrp3-/- mice which are unable to produce mature IL-18, increased mortality and microscopic/macroscopic evidence of colitis was observed compared to WT mice. Disease deterioration could be reversed by the administration of IL-18 indicating a key role for IL-18 in disease prevention in this model.

The conflicting roles for anti-IL-18 reported in the literature may be due in part to the different susceptibilities in the mouse strains used or alternatively the mechanism of induction of colitis in the various models; TNBS induces a Th1 driven colitis in intestinal mucosa, whereas DSS is directly toxic to colonic epithelial cells of the basal crypts. Another hypothesis which has been proposed is that IL-18 exerts a dual role in intestinal homeostasis and colitis. Early in the mucosal immune response expression of IL-18 by IECs plays a role in maintenance of barrier immunity. However under chronic inflammation, and following breach of the intestinal mucosa by bacteria, the cytokine is expressed in the lamina propria; its excessive production results in deleterious effects and drives the expression of a pro-inflammatory cascade (Reuter and Pizarro 2004).

IL-18 is expressed by resident monocytes and macrophages in intestinal epithelial cells and functions as a proinflammatory cytokine, thus contributing to differentiation and activation of T cells. Furthermore, IL-18 upregulates the p38 and JNK MAP kinase's which are known to be important in the pathophysiology of CD. Accordingly, IL-18 offers an attractive target to interrupt inflammation in CD at several points.

Both rare and common human genetic evidence implicate the IL-18 pathway in the development of IBD and CD. Rare gain-of-function mutations in NLRC4, an upstream regulator of IL-18, are known to cause a syndrome of enterocolitis and auto-inflammation (Romberg, Al Moussawi et al. 2014) (Canna, de Jesus et al. 2014). A patient with severe enterocolitis caused by those mutations was successfully treated by inhibiting IL-18 using IL-18BP (Canna, Girard et al. 2017). This clinical study supports the role of IL-18 as a driver of the disease within those patients.

Common SNPs have also been linked to CD and IBD. In previous studies, common variants within the IL-18 promoter have been shown to directly impact its expression (Giedraitis, He et al. 2001) (Liang, Cheung et al. 2005) (Arimitsu, Hirano et al. 2006) (Zhou, Yamaguchi et al. 2005). Subsequent Mendelian randomisation analysis revealed that regulatory variants which increased IL-18 levels were also independently associated with increased risk of CD. This analysis established a causal genetic link between IL-18 levels and CD. In addition to genetic associations with IL-18 levels, genome-wide association studies have also mapped the IL-18RL1/IL-18RAP locus with CD risk (Franke, McGovern et al. 2010) (Jostins, Ripke et al. 2012). The associated SNPs are also correlated with changes in IL-18RL1/IL-18RAP expression levels. Recent unpublished data suggest that there may be additional signals in the receptor locus that require further interrogation. Together, the genetic data provides evidence for a causal link between activation of the IL-18 pathway and increased CD/IBD susceptibility in humans.

1.1.6 Anti-IL-18 monoclonal antibody (GSK1070806)

GSK1070806 is a specific humanised IgG1 antibody that binds to human IL- 18 with high affinity (KD = 30.3pM). GSK1070806 cross reacts with rhesus/cynomolgus IL IL-18 with high affinity (KD = 108 pM), but not mouse, rat, dog or pig IL-18. Biacore analysis and ELISA binding assays have shown that binding of GSK1070806 to IL-18 does not interfere with the binding of the natural endogenous inhibitor (IL-18BP) to IL-18.

1.1.7 Previous Human Experience with GSK1070806

Recognition that IL-18 may play an important role in various diseases has led to the development of investigational therapies targeting IL-18 or its signalling pathways, which have been well tolerated in healthy volunteers and patients with RA, Type 2 diabetes, and plaque psoriasis (Tak, Bacchi et al. 2006) (Mistry, Reid et al. 2014).

To date GSK1070806 has been administered to 89 participants.

In volunteers, single intravenous infusion doses of the anti-IL-18 monoclonal antibody, GSK1070806, were well tolerated in both healthy and obese participants (NCT01035645). No differences in infections, immune system disorders or haematological abnormalities were observed following single intravenous GSK1070806 infusions up to 10 mg/kg in 57 participants when compared with placebo. Four participants had serious adverse events (SAEs) (head injury, mild pericarditis (placebo group), kidney stones, and pneumothorax) that were all considered unrelated to study treatment by the Investigator (Mistry, Reid et al. 2014).

GSK1070806 was also evaluated in patients with type 2 diabetes (NCT01648153) (McKie, Reid et al. 2016), in which in two cohorts two repeat doses of GSK1070806 (0.25 and 5 mg/kg), administered 28 days apart, were well-tolerated in 25 patients when compared with placebo. The most frequently reported adverse event (AE) was nasopharyngitis which occurred in 11 participants. Headache, diarrhoea and hypertension were the second most frequently reported AEs, which occurred in 5 participants each. None of the reported AEs was considered related to GSK1070806. The most frequently reported MedDRA system organ class was 'Infections and Infestations'.

Single administration of 3mg/kg in 7 patients (followed by 10mg/kg after interim analysis) GSK1070806 is also being evaluated in an on-going Phase 2 single arm open label study for the prevention of Delayed Graft Function in Adult participants after renal transplantation(NCT02723786).

1.1.8 Patient Population Specific Information

Conflicting roles of IL-18 in gut mucosal protection have been reported in the literature (based on murine experiments). Patients will therefore undergo endoscopy prior to dosing and at 12 weeks. Endoscopy at screening will enable a visual assessment of the gut mucosa and any worsening of disease can be identified and treated accordingly using standard of care (SOC). The exclusion of patients with deep penetrating complications such as fistulae, plus the inclusion of a daily diary (diarrhoea and abdominal pain) in the trial should aid in the early identification of any worsening of symptoms.

For further information relating to GSK1070806 please refer to the current Investigator Brochure.

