Exclusion Criteria	1. Written informed consent prior to any of the screening procedures including discontinuation of prohibited medications. (see Section 7.11 for additional information)
	 Patients must have been diagnosed with Crohn's disease at least 3 months prior to Screening Visit 1
	 Patients are required to have endoscopic evidence of active Crohn's disease at Baseline defined by endoscopic appearance: SES-CD excluding the narrowed component of ≥ 6 (or ≥4 for patients with isolated ileal disease).
	 AST and ALT ≤ 2xULN; alkaline phosphatase and bilirubin ≤ 1.5xULN (isolated bilirubin >1.5xULN is acceptable if bilirubin is fractionated and direct bilirubin <35%)
	5. Male or female participants aged ≥ 16 years (up to 80 years)
	See Section 4 for complete list of inclusion criteria
	Exclusion Criteria
	1. Diagnosis of ulcerative or indeterminate colitis
	Crohn's disease complications:
	2. Evidence of an infected abscess by MRI or other examinations
	3. Bowel surgery other than appendectomy within 12 weeks prior to screen and/or has planned surgery or deemed likely to need surgery for CD during the trial period
	 Participants with ileostomies, colostomies or rectal pouches Participants with a bowel stricture that is fixed Participants with evidence of short bowel syndrome

	7. Participants requiring enteral or parenteral feeding
	8. Deep penetrating ulcers at endoscopy thought to be at risk for perforation.
	See Section 4 for complete list of exclusion criteria
Permitted Concomitant Medication	 Oral Corticosteroids: For participants receiving prednisone, or equivalent, the dose must be ≤20mg/day for ≥4 weeks prior to screening and planned to remain stable for the duration of the trial. For participants receiving
	budesonide the dose must be $\leq 6 \text{mg/day}$ for ≥ 4 weeks prior to screen and planned to remain stable for the duration of the study
	2. Immunosuppressant and other Crohn's disease medications: For participants receiving azathioprine, methotrexate, or 6-mercaptopurine for Crohn's disease, the dose must be stable for >8 weeks prior to screening and planned to remain stable for the duration of the study. For participants receiving methotrexate or 5-aminosalicyclic acid for Crohn's disease, the dose must be stable for >4 weeks prior to screening and planned to remain stable for the study.

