1. BACKGROUND AND RATIONALE

1.1 Background

1.1.1 Crohn's Disease

Crohn's disease (CD) is a chronic systemic disorder involving the gastrointestinal tract. Patients with Inflammatory Bowel Disease (IBD) can present with a range of symptoms including diarrhoea and abdominal pain, tenesmus or rectal bleeding reflecting the anatomic location of disease [Lichtenstein et al, 2009]. CD is characterised by focal, asymmetric, transmural inflammation affecting the small and large intestines (Lichtenstein, Yip et al. 2009).

The incidence and prevalence of CD in western populations is about 50 per 100,000 (Ng, Shi et al. 2018). The most common age for first diagnosis is 15-30 years and in some studies there is a female preponderance. (Lichtenstein, Yip et al. 2009, Cosnes, Gower-Rousseau et al. 2011) (Molodecky, Soon et al. 2012).

CD is heterogeneous in the location of intestinal involvement and disease course. The Montreal classification, attempted to phenotype patients with CD by disease location (ileal, colonic, ileocolonic or isolated upper intestinal) and by evolution (stricturing, penetrating (fistulas and abscesses) or non-stricturing, non-penetrating). Longitudinal studies indicate the anatomic location of disease is relatively stable over time (with about 47% ileal, 28% colonic and 21% ileocolonic at first presentation) and less than 20% of patients with small bowel disease developing colonic disease and vice versa over 10 year follow up (Baumgart and Carding 2007) (Cosnes, Gower-Rousseau et al. 2011). It is increasingly clear that disease behaviour is dynamic over time and patients with predominantly inflammatory disease at diagnosis are very likely to develop either fistulising or stricturing complications during follow up (Cosnes, Gower-Rousseau et al. 2011) (Satsangi, Silverberg et al. 2006) so that CD is progressive. CD evolution relates to disease location. Small bowel involvement is associated with higher rates of penetrating or other complications, whereas colonic disease can remain uncomplicated or inflammatory for many years (Cosnes, Gower-Rousseau et al. 2011).

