After the first year from diagnosis, 10–30% of patients with CD have an exacerbation, 15–25% have low activity, and 55–65% are in remission. Around 15–20% of patients with CD have a chronic active course of disease activity, 67–73% have a chronic intermittent course and only 10–13% remain in remission for several years. After 20 years, most patients with CD will have undergone surgery (Ma, Moran et al. 2017) to resect inflamed bowel (not responding to medical treatment), relief of obstruction, abscess drainage or fistula excision and closure. The life expectancy of patients with CD is slightly reduced (Baumgart and Carding 2007).

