4. ELIGIBILITY

4.1 Inclusion Criteria

A patient will be eligible for inclusion in this study only if all of the following criteria apply:

- 1. Written informed consent prior to any of the screening procedures including discontinuation of prohibited medications. (see Section 7.11 for additional information)
- 2. Patients must have been diagnosed with Crohn's disease at least 3 months prior to Screening Visit 1
- 3. Patients are required to have endoscopic evidence of active Crohn's disease at Baseline defined by endoscopic appearance: SES-CD excluding the narrowed component of \geq 6 (or \geq 4 for patients with isolated ileal disease).
- 4. AST and ALT \leq 2xULN; alkaline phosphatase and bilirubin \leq 1.5xULN (isolated bilirubin >1.5xULN is acceptable if bilirubin is fractionated and direct bilirubin <35%)
- 5. Male or female participants aged \geq 16 years (up to 80 years)

Male participants:

6. A male participant must agree to use contraception as detailed in Appendix 5 of this protocol for at least 180 days post-dose of study medication and refrain from donating sperm during this period.

Female participants:

- 7. If the patient is breastfeeding, she must agree to stop breastfeeding once randomised into the trial. ¹
- 8. A patient is eligible to participate if she is not pregnant.
- 9. A woman of childbearing potential (WOCBP) is eligible only if she meets at least one of the following conditions:
 - Females on HRT and whose menopausal status is in doubt will be required to use one of the non-hormonal highly effective contraception methods if they wish to continue their HRT during the trial. Otherwise, they must discontinue HRT to allow confirmation of postmenopausal status before trial enrolment.
 - Agrees to follow the contraceptive guidance in Appendix 5 for at least 180 days post-dose of trial medication. If a hormonal method of birth control is selected from the list in Appendix 5 then patients must have been using these methods at least 1 month prior to GSK1070806 administration, or be abstinent, or utilise a condom as a method of contraception until the selected hormonal method has been in place for the 28 day period.
- 10. A woman who is not of childbearing potential is eligible only if she meets at least one of the following conditions:
 - i. Premenopausal female with documented hysterectomy
 - ii Premenopausal female with documented bilateral salpingectomy or oophorectomy

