4.2 Exclusion Criteria

A participant will not be eligible for inclusion in this trial if any of the following criteria apply:

1. Diagnosis of ulcerative or indeterminate colitis

Crohn's Disease complications:

- 2. Evidence of an infected abscess by MRI or other examinations
- 3. Bowel surgery other than appendectomy within 12 weeks prior to screen and/or has planned surgery or deemed likely to need surgery for CD during the trial period
- 4. Participants with ileostomies, colostomies or rectal pouches
- 5. Participants with a bowel stricture that is fixed
- 6. Participants with evidence of short bowel syndrome
- 7. Participants requiring enteral or parenteral feeding
- 8. Deep penetrating ulcers at endoscopy thought to be at risk for perforation

Viral and bacterial infections:

- Presence of Hepatitis B surface antigen (HBsAg), (confirmed by Hepatitis B surface antigen test within 12 months of randomisation) core antigen (HBcAg) or surface antibody (HBsAb), positive Hepatitis C (qualitative enzyme immunoassay) test result
- 10. Known varicella, herpes zoster, or other severe viral infection within 6 weeks of randomisation
- 11. The participant has a history of tuberculosis (TB) disease or latent TB infection, in the absence of documented adequate therapy for same.
- 12. Positive screening test for TB (including T-SPOT.TB TB test), unless respiratory review confirms false positive test results
- 13. History of uncontrolled bacterial or fungal infection requiring intravenous antibiotics
- 14. Positive immunoassay for *Clostridium difficile* toxin and other enteric pathogens

Other exclusion criteria:

- 15. Cardiology assessment/co-morbidity defined as:
- i. QTc >450 msec (480msec for those with Bundle Branch Block) and/or
- ii. either QTcb or QTcf, machine or manual overread, males or females. The QT correction formula used to determine exclusion and discontinuation should be the same throughout the trial and/or
- iii. based on single QTc value (average of triplicate readings) of ECG obtained over a brief recording period
- 16. The participant has congenital or acquired immunodeficiency, or a history of chronic or recurrent opportunistic infections
- 17. The participant has current evidence of, or has been treated for a malignancy within the past five years (other than localised basal cell, squamous cell skin cancer, cervical dysplasia, or cancer in situ that has been resected)

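### Section 1.1.8 says patients with fistulae are excluded, but no eligibility criterion excludes them, so such a patient can be randomised and dosed

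*Protocol*

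**What the plan says.** Protocol Section 1.1.8 opens with the conflicting murine evidence on whether IL-18 protects the gut mucosa. It provides for endoscopy before dosing and at week 12, and then refers to "The exclusion of patients with deep penetrating complications such as fistulae, plus the inclusion of a daily diary" of symptoms, which together "should aid in the early identification of any worsening of symptoms". The exclusion is written as something the trial already has.

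The synopsis gives eight exclusions and then directs the reader onward: "See Section 4 for complete list of exclusion criteria". Section 4.2 has 20 criteria. Its block on Crohn's complications (criteria 2 to 8) covers infected abscess, bowel surgery, stomas and pouches, fixed stricture, short bowel syndrome, enteral or parenteral feeding, and deep ulcers thought to risk perforation. Fistula is not among them.

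Under Section 6.1 the site confirms the inclusion criteria, reviews the exclusion criteria and completes the eligibility form before randomising.

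**The concern.** The population that the protocol describes is not the one its criteria select. Section 1.1.8 tells ethics, regulatory and monitoring-committee readers that patients with fistulae stay out. A site that follows Section 4 exactly may let them in.

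This matters more here than in a trial of an established drug. Safety, including infections, is the primary outcome. Section 1.2.3 calls IL-18 an unprecedented target in Crohn's disease, and the dose was chosen to suppress it almost completely in the gut for 90 days. Treatment is one infusion (Section 7.7.4), so an eligibility safeguard works before dosing or not at all.

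The case is also plausible on the protocol's own account. Inclusion criterion 2 sets only a minimum time since diagnosis, "at least 3 months prior to Screening Visit 1". Section 1.1.1 says that patients whose disease is mainly inflammatory at diagnosis are "very likely to develop either fistulising or stricturing complications during follow up".

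**Working it through.** The point is textual, so the check sets the statement beside every place that could give it effect.

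**Step 1: search for the exclusion.**
- Section 4.2: 0 of 20 criteria name fistula or penetrating disease as such.
- Synopsis: 0 of 8.
- Section 4.1: requires a minimum time since diagnosis and an SES-CD threshold, but not non-penetrating disease.
- Section 3.1: no mention.
- Section 7.11.2, to which criterion 20 refers: medications and therapies only.
- Outside Section 1.1.8, fistula appears only as disease background, in Sections 1.1.1 and 1.1.2.

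**Step 2: see whether neighbouring criteria do the same job.** Section 1.1.1 sets out disease evolution as stricturing, "penetrating (fistulas and abscesses) or non-stricturing, non-penetrating". That names three complications. Section 4.2 has a criterion for two of them and none for the third:
- Abscess: criterion 2, "Evidence of an infected abscess by MRI or other examinations". A fistula without an infected abscess passes.
- Stricture: criterion 5, fixed strictures only.
- Fistula: none.

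Two further criteria overlap in part:
- Criterion 3 removes patients whose bowel surgery is recent, planned or thought likely. Section 1.1.1 lists "abscess drainage or fistula excision and closure" among the reasons for surgery, so this catches some fistula patients, but not one managed without surgery.
- Criterion 8 removes deep ulcers seen at endoscopy and judged to risk perforation. An established fistula, for example a perianal one, is not such an ulcer. This is the only penetrating finding at endoscopy that Section 4.2 uses.

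Criteria 4, 6 and 7 (and 5, where a fixed stricture coexists) may remove others incidentally. What remains is a patient with a fistula who meets none of these, and nothing in Section 4 keeps that patient out.

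**Step 3: see whether another step applies Section 1.1.8.** Section 6.1 ties randomisation to the listed criteria and the eligibility form. No step refers a site to the background text.

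**Step 4: size.** The protocol gives no fistula prevalence. As an illustration, let p be the share of otherwise eligible patients with a fistula that no other criterion catches. The values of p are assumed, and patients are treated as independent. With n = 21, the chance of at least one such patient is 1 − (1 − p)^21:
- p = 1%: 1 − 0.99^21 = 0.190
- p = 5%: 1 − 0.95^21 = 0.659
- p = 10%: 1 − 0.90^21 = 0.891

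**The case against.** The strongest reply is that Section 1.1.8 loosely paraphrases criteria 2, 3 and 8. Its reference to deep penetrating complications echoes criterion 8, and the complications block in Section 4.2 looks deliberate and narrow: infected abscess only, fixed stricture only. On that reading the criteria are what the sponsor wants and the fault is one imprecise background phrase. The text does not rule this out. It does not clear the protocol either: fistulae are the one example Section 1.1.8 names, and a paraphrase that names a group the criteria admit is still wrong.

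Several narrower objections stand and limit the claim:
- Section 1.1.8 gives early detection of worsening as the purpose. It does not say that fistula patients face a special risk from the drug. The measure it links directly to the IL-18 evidence is endoscopy, which is scheduled, as is the diary. The argument from the single infusion is this review's, not the protocol's.
- The prognosis in Section 1.1.1 combines fistulising and stricturing disease over long follow-up. It is not a frequency at screening.
- Section 1.1.1 groups fistulas and abscesses in one penetrating category, so counting two of three complications is only a way of showing the gap.
- The probabilities rest on assumed values of p, and the presence of one such patient is not a measure of harm.
- The content of the Eligibility Checklist is not shown; Table 9 only lists the form.

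Whether these patients ought to be excluded is a clinical decision. The mismatch is an error whichever way that decision goes.

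**Conclusion.** The concern holds. Section 1.1.8 reports an exclusion that the protocol nowhere applies, and a site complying fully with Section 4 can dose a patient whom the protocol says is excluded. This rests on the text alone: no fistula criterion among the 20 in Section 4.2 or the 8 in the synopsis, and only partial cover from criteria 2, 3 and 8. The number of patients affected is unknown; the 19% to 89% range depends entirely on the assumed p of 1% to 10%, and the conclusion does not need it. No endpoint, analysis or sample-size figure changes. What changes is who may receive the drug in a small safety trial, so this should be fixed.

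**What to change.** Add an exclusion to Section 4.2, and repeat it in the synopsis and the Eligibility Checklist, for known or endoscopically evident fistulising or penetrating Crohn's disease. State whether perianal fistula is covered. Base it on the Crohn's history taken at Screening Visit 1 (Section 5.2.1) and the screening endoscopy, both already scheduled.

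If the sponsor does not intend this exclusion, reword Section 1.1.8 so that it describes only what criteria 2, 3 and 8 remove.

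The cost is one line in each of three places, or one sentence in Section 1.1.8, with no new procedure. The added criterion would leave slightly fewer eligible patients. Occult fistulae would still be missed, because the Schedule of Events contains no cross-sectional imaging.
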